7.3.4. Updating of SAE information after freezing of the subject's eCRF

When additional SAE information is received after freezing of the subject's eCRF, new or updated information should be recorded on a paper Expedited Adverse Event Report, with all changes signed and dated by the investigator. The updated report should be faxed to the GSK Biologicals Clinical Safety and Pharmacovigilance department or to the Study Contact for Reporting SAEs (see the [Sponsor Information](#)) within the designated reporting time frames specified in [Table 16](#).

7.3.5. Regulatory reporting requirements for SAEs

The investigator will promptly report SAEs related to study participation to GSK Biologicals in accordance with the procedures detailed in Section 7.3.1. GSK Biologicals has a legal responsibility to promptly notify, as appropriate, both the local regulatory authority and other regulatory agencies. Prompt notification of SAEs related to study participation by the investigator to the Study Contact for Reporting SAEs is essential so that legal obligations and ethical responsibilities towards the safety of other subjects are met.

7.4. Follow-up of SAEs related to study participation**7.4.1. Follow-up of SAEs related to study participation****7.4.1.1. Follow-up during the study**

After the initial SAE report, the investigator is required to proactively follow each subject and provide further relevant information on the subject's condition to GSK Biologicals (within 24 hours for SAEs, refer to [Table 16](#)).

All SAEs related to study participation documented at a previous visit/contact and recorded as not recovered/not resolved or recovering/resolving will be reviewed at subsequent visits/contacts until the end of the study.

7.4.1.2. Follow-up after the subject is discharged from the study

The investigator will follow-up subjects with SAEs related to study participation, until the event has resolved, subsided, stabilised, disappeared, or until the event is otherwise explained, or the subject is lost to follow-up.

If the investigator receives additional relevant information on a previously reported SAE, he/she will provide this information to GSK Biologicals using a paper Expedited Adverse Event Report.

GSK Biologicals may request that the investigator performs or arranges for the conduct of additional clinical examinations/tests and/or evaluations to elucidate as fully as possible the nature and/or causality of the SAE. The investigator is obliged to assist. If a subject dies during participation in the study or during a recognised follow-up period, GSK Biologicals will be provided with any available post-mortem findings, including histopathology.

8. SUBJECT COMPLETION AND WITHDRAWAL**8.1. Subject completion**

A subject who returns for the concluding visit/is available for the concluding contact foreseen in the protocol is considered to have completed the study.

8.2. Subject withdrawal

Subjects who are withdrawn because of SAEs related to study participation must be clearly distinguished from subjects who are withdrawn for other reasons. The investigator will follow subjects who are withdrawn as the result of an SAE related to study participation until resolution of the event (see Section [7.4.1.2](#)).

Withdrawals will not be replaced.

From an analysis perspective, a ‘withdrawal’ from the study refers to any subject who did not come back for the concluding visit/was not available for the concluding contact foreseen in the protocol.

All data collected until the date of withdrawal/last contact of the subject will be used for the analysis.

A subject is considered a ‘withdrawal’ from the study when no study procedure has occurred, no follow-up has been performed and no further information has been collected for this subject from the date of withdrawal/last contact.

If no adult household member can be reached during a weekly contact (home visit or TC), 3 additional attempts to contact the household should be made on the 3 days following the initial attempted contact. If after a period of 4 weeks, the household can still not be contacted, its members will be considered as a lost to follow-up (see below). Each attempt to contact a household should be documented.

Investigators will make an attempt to contact those subjects who do not return for Visit 2 or for Suspected Dengue Follow-up Visits.

Information relative to the withdrawal will be documented in the eCRF. The investigator will document whether the decision to withdraw a subject from the study was made by the subject himself/herself, by the subject’s parent(s)/LAR(s), or by the investigator, as well as which of the following possible reasons was responsible for withdrawal:

- SAE*
- Protocol violation (specify)
- Consent (or assent when applicable) withdrawal, not due to an SAE**
- Moved from the study area
- Lost to follow-up***
- Other (specify)

* Subjects who are withdrawn from the study because of SAEs related to study participation must be clearly distinguished from subjects who are withdrawn for other reasons. Investigators will follow subjects who are withdrawn from the study as result of an SAE related to study participation until resolution of the event (see Section [7.4.1.2](#)).

**In case a subject is withdrawn from the study because he/she/the subject's parent(s)/LAR(s) has withdrawn consent (or assent when applicable), the investigator will document the reason for withdrawal of consent (or assent when applicable), if specified by the subject/the subject's parent(s)/LAR(s), in the eCRF.

*** Subjects who cannot be contacted (via home visits/TCs or visits at study hospital/clinic) during 4 consecutive weeks will be considered as lost to follow-up. Subjects lost to follow-up will only be replaced during the enrolment period.

8.3. Extension study

The sponsor may decide to extend the study for a specified time period. This would be detailed in a protocol amendment and the subject will be asked to sign a new ICF (or IAF when applicable).

If so, at the end of the study (study conclusion visit/contact), the investigator will ask each subject/subject's parent(s)/LAR(s) if they are interested in participating/allowing the subject to participate in future studies. If a subject/subject's parent(s)/LAR(s) is/are not interested in participating in future studies the reason for refusal will be documented in the subject's eCRF.

9. STATISTICAL METHODS

9.1. Endpoints

9.1.1. Primary endpoint

- Occurrence of AFI due to LCD.

Please refer to Section 4 for the case definitions of AFI due to LCD.

9.1.2. Secondary endpoints

- Occurrence of AFI due to non-LCD.
- Occurrence and intensity of signs and symptoms of interest, during the 7-day period following the onset of each episode of AFI due to LCD and due to non-LCD.
- Occurrence of AFI due to LCD by DENV type, study site, and age group.

Please refer to Section 4 for the case definitions of AFI due to LCD and due to non-LCD.

9.1.3. Tertiary (research) endpoints

During the Suspected Dengue First Visit, additional blood volumes will be collected for tertiary study endpoint assays. These tertiary study endpoints include, but are not limited to, determination of neutralising antibody titres against dengue virus (DENV), Japanese encephalitis virus (JEV), and chikungunya virus, tissue culture to isolate infectious agents, and sequencing to characterise infectious agents. **(Amended 01 March 2017)**

Tertiary study endpoint assays *may* be performed for a subset of samples (for example, JEV assays will only be conducted if additional studies indicate that JEV serology is needed to interpret the DENV antibody response), i.e., not all of these endpoint assays will be performed on all of the sera collected from adult study subjects. **(Amended 01 March 2017)**

Research objectives may be assessed based on, but not limited to, the following endpoints: **(Amended 01 March 2017)**

- Neutralising antibody titres against JEV.
- Neutralising antibody titres against other viruses, including but not limited to, Chikungunya virus.
- Incidence of NS1-antigen (ICT test and/or ELISA)-positive AFI by DENV type.
- Concordance between dengue RT-qPCR and NS1-antigen (ICT and/or ELISA) assays.
- Occurrence of AFI due to LCD and due to non-LCD having (\geq 3 days of fever (body temperature (\geq 38°C/ \geq 100.4°F).
- Occurrence of AFI due to LCD and due to non-LCD resulting in hospitalisation.
- Occurrence of combinations of signs and symptoms during the 7-day period following the onset of each episode of AFI due to LCD and due to non-LCD.
- Occurrence of AFI due to LCD within 2 weeks from an index case, in the same household or within 50 metres of the household of the index case.
- Entomological characteristics for LCD cases (e.g., vector species, density and number of breeding sites) at selected site(s).
- Occurrence (by medical history only) of a diagnosis of tuberculosis, from birth up to study conclusion, in the study population.
- Occurrence of hospitalisation and discharge diagnosis.
- Identification and characterisation of infectious agents isolated from blood (e.g., DENV, influenza viruses, chikungunya viruses), in subjects with AFI.

Please refer to Section 4 for the case definitions of AFI due to LCD and due to non-LCD.

9.2. Sample size considerations

A **maximum of 2,000** subjects will be enrolled for a 2-year follow-up period. Assuming a drop-out rate of 10% the first year and a drop-out rate of 20% the second year, the final analysis will be done on approximately **3300** person-years overall.

In order to evaluate the precision with a sample size of **3,000** subjects, the 95% confidence interval (CI) (Poisson exact distribution and normal approximation of the Poisson distribution accounting for a design effect) for a range of expected incidences rates of AFI due to LCD were computed. The 95% CI for a range of expected incidences rates for DENV specific LCD were also presented (see [Table 17](#)).

(Amended 01 March 2017)

Estimating design effect and precision

The normal approximation of the Poisson distribution was used for calculating 95% CI for this cluster design. The variance was adjusted for a design effect of 2.6 to account for the between-cluster variability. The design effect measures the increase in the standard error of the estimate due to the sampling design used and is given by: $D = 1 + (b - 1) \rho$, where ρ is the rate of homogeneity (a measure of variability and equivalent to the “intra-cluster correlation”) and b is the average number of subjects sampled per household. Here we assumed b to be 5. Although, in theory ρ can have a value up to 1, in practice values higher than 0.4 are uncommon [Bennett, 1991]. We used a conservative estimate of 0.4 for this study. The design effect is then estimated to 2.6.

Table 17 95% CI with design effect of 2.6

	Number of cases	Number of person-years	Incidence of LCD (per 100 person-years)	95% CI Poisson exact		95% CI Normal approx with design effect of 2.6	
				LL	UL	LL	UL
Overall	10	3300	0.30	[0.15 ; 0.56]		[0.00 ; 0.61]	
	20	3300	0.61	[0.37 ; 0.94]		[0.18 ; 1.03]	
	30	3300	0.91	[0.61 ; 1.30]		[0.38 ; 1.43]	
	40	3300	1.21	[0.87 ; 1.65]		[0.61 ; 1.82]	
	50	3300	1.52	[1.12 ; 2.00]		[0.84 ; 2.19]	
	60	3300	1.82	[1.39 ; 2.34]		[1.08 ; 2.56]	
DENV specific	4	3300	0.12	[0.03 ; 0.31]		[0.00 ; 0.31]	
	8	3300	0.24	[0.10 ; 0.48]		[0.00 ; 0.51]	
	12	3300	0.36	[0.19 ; 0.64]		[0.03 ; 0.70]	
	16	3300	0.48	[0.28 ; 0.79]		[0.10 ; 0.87]	

(Amended 01 March 2017)

CI: confidence interval**DENV:** dengue virus**LCD:** laboratory Confirmed Dengue**LL:** lower limit;**UL:** upper limit

At time of analysis, the design effect of this study will be estimated using the following formula [Bennett, 1991]:

$$DE = \frac{s^2_{\text{CLUSTER SAMPLE}}}{s^2_{\text{SIMPLE RANDOM SAMPLE}}}$$

With

$$s^2_{\text{CLUSTER SAMPLE}} = (c/\sum x_i)^2 (\sum y_i^2 - 2p \sum x_i y_i + p^2 \sum x_i^2) / [c(c-1)]$$

$$s^2_{\text{SIMPLE RANDOM SAMPLE}} = p(1-p)/n$$

Where, c is the number of clusters, x_i and y_i are the number of person-years and the number of cases, respectively in the i^{th} cluster, n is the total number of person-years and p is the overall proportion $\sum y_i / \sum x_i$.

The intra-cluster correlation ρ may then be estimated as:

$$\rho = (DE - 1) / [(\sum x_i/c) - 1]$$

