9.2. Statistical Method

9.2.1. Computation of incidence rate

The incidence rate of first event (IR, number of first episodes per 1000 person-years) will be calculated by dividing the number of subjects reporting at least one episode of event during the follow-up period by the total person-year at risk.

The person-time at risk for an event of interest (e.g. AFI due to LCD) will be calculated as the duration between the date of enrolment and the end of the at-risk period or the earliest of the following:

- Onset date of event of interest (e.g. first episode of AFI due to LCD)
- Date of last contact
- Date of death.

9.2.2. The method for estimating the CIs for incidence rate not accounting for clustered data

To estimate the confidence interval of the incidence rate, the exact Poisson confidence interval will be used [Clopper, 1934].

If n is the number of subjects presenting a given characteristic among these Ny subjects per year, the true incidence rate per 1000 person-years can be estimated by $(n/Ny)*1000$. Its exact $(1-\alpha)\%$ confidence interval is obtained from:

$CINV(\alpha/2, 2*n)/2/Ny*1000$ as the lower boundary

and

$CINV((1-\alpha)/2, 2*(n+1))/2/Ny*1000$ as the upper boundary.

where $CINV$ (*probability, degrees of freedom*) returns the inverse of the chi-squared probability distribution and α is the type I error rate, which will be 0.05 for calculating a 95% CI.

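### Given the protocol's own design effect of 2.6, the adjusted upper limits in Table 17 are too low at small case counts, because a symmetric normal interval is used.

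*Protocol*

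**What the plan says.** Protocol section 9.2 presents the study's precision in Table 17. For each hypothetical case count in 3300 person-years, the table gives an exact Poisson interval that ignores clustering, and a second interval meant to allow for household sampling. On the second, the text says: "The normal approximation of the Poisson distribution was used for calculating 95% CI for this cluster design", and "The variance was adjusted for a design effect of 2.6 to account for the between-cluster variability". The design effect comes from two assumptions, an average household sample ("Here we assumed b to be 5") and an intra-cluster correlation ("We used a conservative estimate of 0.4 for this study"). The denominator, "approximately 3300 person-years overall", follows from planned enrolment and assumed drop-out.

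For 4 cases of one DENV type, the two printed intervals are 0.03 to 0.31 (exact) and 0.00 to 0.31 (adjusted). For 8 cases they are 0.10 to 0.48 and 0.00 to 0.51. Section 9.2 does not say that negative lower limits were set to zero, and gives no caution about small counts. Incidence by DENV type is a secondary objective (protocol section 2.2).

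**The concern.** A design effect of 2.6 raises the standard error by √2.6 = 1.61. It is therefore odd that at 4 cases the adjusted upper limit is the same as the unadjusted one, and at 8 cases only slightly higher. A reader comparing the two columns on the upper side would conclude that clustering hardly affects what can be said about a rare serotype. A lower limit of 0.00 is also odd when cases have been observed.

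What is at stake is the stated precision for the sparse rows. Protocol section 3.1 says that the study is to supply incidence data for sizing later efficacy trials, so a reader may use Table 17 to judge how high a type-specific rate could plausibly be.

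**Working it through.** **Inputs (protocol section 9.2).** Household size b = 5, correlation 0.4, person-years 3300, 95% two-sided (z = 1.96). Design effect D = 1 + (5 − 1) × 0.4 = 2.6. Rates are per 100 person-years, so a count is divided by 33.

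**Reproducing the table.**
- Exact column: χ²(0.025; 2n)/2 and χ²(0.975; 2(n + 1))/2, each divided by 33. At n = 4 this gives 0.033 to 0.310.
- Adjusted column: (n ± 1.96√(2.6n))/33. At n = 4: (4 ± 6.32)/33 = −0.070 to 0.313. At n = 8: (8 ± 8.94)/33 = −0.028 to 0.513.

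All ten rows match to rounding once the negative limits are set to 0.00. Only the 4- and 8-case rows are cut in this way; at 10 cases the lower limit is 0.0002 and simply rounds to 0.00.

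**Why the 4-case upper limits coincide.** An unadjusted normal upper limit would be (4 + 1.96√4)/33 = 0.24. The design effect raises this to 0.31. The exact interval reaches 0.31 without any adjustment because it is skewed upward. What the adjustment adds is offset by the skewness that the symmetric form leaves out.

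**Same design effect, three forms that respect skewness.**
- Exact limits on the effective count (n/2.6 cases in 3300/2.6 person-years): χ²(0.025; 2n/D)/2 × D/33 and χ²(0.975; 2(n/D + 1))/2 × D/33.
- Score interval with variance times 2.6: [n + z²D/2 ± √(z²D(n + z²D/4))]/33. At n = 4, z²D = 9.99, so (8.99 ± 8.06)/33 = 0.03 to 0.52.
- Log scale: (n/33) × exp(±1.96√(2.6/n)). At n = 4, 0.121 × exp(±1.58) = 0.02 to 0.59.

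| Cases | Exact upper, no clustering | Table 17 adjusted upper | Effective count | Score | Log scale |
|---|---|---|---|---|---|
| 4 | 0.31 | 0.31 | 0.51 | 0.52 | 0.59 |
| 8 | 0.48 | 0.51 | 0.70 | 0.70 | 0.74 |
| 12 | 0.64 | 0.70 | 0.88 | 0.88 | 0.91 |
| 16 | 0.79 | 0.87 | 1.05 | 1.05 | 1.07 |
| 40 | 1.65 | 1.82 | 1.99 | 1.99 | 2.00 |
| 60 | 2.34 | 2.56 | 2.73 | 2.73 | 2.73 |

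With the effective-count form, the unrounded 4-case limit is 0.511 against 0.313, or 63% higher. At 60 cases it is 2.726 against 2.560, or 6.5% higher. The lower limits move the other way: at 4 cases the alternatives give 0.01 to 0.03 and at 8 cases 0.05 to 0.08, where Table 17 prints 0.00.

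**Coverage.** The assumption is negative-binomial counts with variance 2.6 times the mean, 400,000 draws per mean.

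| Expected cases | Coverage of Table 17 method | Truth above upper limit |
|---|---|---|
| 8 | 91.3% | 8.2% |
| 12 | 93.2% | 6.2% |
| 16 | 92.0% | 7.2% |
| 20 | 91.4% | 7.6% |

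Nominal values are 95% and 2.5%. In the same setting, the score interval covers about 95 to 96% at 4 to 20 expected cases, and the effective-count interval about 97 to 98%.

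**The case against.** Several objections have force.

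- **No arithmetic error.** Section 9.2 names the method, and the exact interval stands beside the adjusted one. This is right: the fault is in the choice of approximation.
- **The table does show a clustering cost.** A reader might infer from the 4-case row that Table 17 makes clustering look free throughout. It does not. From 8 cases up the lower limit drops clearly (0.10 to 0.00 at 8, 0.28 to 0.10 at 16). The printed width rises from 0.51 to 0.77 at 16 cases and from 0.78 to 1.21 at 40. Only at 4 cases (0.28 to 0.31) is there almost no change.
- **Coverage at an expected 4 cases is misleading.** The same simulation shows the truth above the upper limit in about 9% of draws there. The chance of zero cases is (1/2.6)^(4/1.6) = 9.2%, and a zero count, for which the formula returns 0 to 0, accounts for all of those misses. Table 17 has no zero row, so that figure is not used here.
- **The effective-count limits over-cover.** They are on the cautious side. The score limits, with close to nominal total coverage, still give almost the same upper limits.
- **Everything is conditional on 2.6.** The protocol calls its correlation conservative. With a smaller true design effect, the printed upper limits need not be too low.

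A reader might also infer that the reported incidence intervals will share this defect. The documents do not support that. SAP section 9.2.2, headed "The method for estimating the CIs for incidence rate not accounting for clustered data", uses exact Poisson limits. The protocol says that the design effect will be estimated at analysis, but neither document specifies an adjusted interval to go with it.

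**Conclusion.** The point holds as a matter of method and presentation. Taking the protocol's design effect of 2.6 as given, the adjusted upper limits in Table 17 are too low. The shortfall is large at 4 cases, still material at 8 to 16, and small at 60. Three different forms agree on the direction and nearly agree on the size from 8 cases upward. The uncut lower limits err downward, so the interval as a whole sits too low. The coverage shortfall is modest (about 2 to 4 percentage points at 8 to 20 expected cases) and rests on the negative-binomial assumption.

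The consequence is limited. Protocol section 9.9 states that there is no confirmatory objective with a success criterion. The enrolment figure follows from the cancellation of the India sites described in the Amendment 3 rationale, and no sample size was derived from these rows. It would be wrong to infer that the study is undersized or that a conclusion is overturned.

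**What to change.** Recompute the last column of Table 17, keeping D = 2.6, with an interval that respects skewness, and name the method in the text and the column header. Two forms are suitable: the score interval with variance times 2.6, whose total coverage is close to nominal, or the exact limits on the effective count, which are slightly conservative. Either form removes the negative lower limits. If the normal form is kept, add a footnote that negative limits are set to zero and that the adjusted upper limits are too low at small counts.

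The cost is one recomputed column and a sentence of text. The stated upper limits become less favourable, chiefly in the DENV-specific rows. Data collection, sample size and the SAP's analyses are unaffected.

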5.1.1. Selection of communities and households

This study will enrol subjects in selected communities based on the following non-exclusive characteristics:

- preferably in areas where access to the community is already established (previous community-based surveillance studies)
- in areas with a high population density
- in areas with low out-migration rate
- in areas with preferably a single point-of-care for the community
- preferably in areas where there is a confirmation of dengue endemicity
- in areas where children are likely to constitute at least 30% of the study population per site
- in households with at least one child (less than 18 years of age)
- in households with at least one adult (aged no more than 50 years) and one child (aged less than 18 years) consenting (and assenting if applicable) to participate in the study

Refer to Section 5.1.2 for an overview of the recruitment plan.
(Amended 01 March 2017).

A list of all households in the sampling area will be generated by each site. Simple random sampling will be performed to select households for enrolment. If the sampling area is too large to compile a list of all households, at least eight clusters of similar population size (blocks or streets) will be selected by simple random sampling. Households in the selected clusters will then be listed and selected by simple random sampling.

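### The design effect counts household clustering only and the analysis formula does not name its cluster unit, so intervals will be too narrow if blocks or streets were sampled first and the formula is run on households

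*Protocol*

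**What the plan says.** Protocol 9.2 defines the planning cluster as the household: "b is the average number of subjects sampled per household. Here we assumed b to be 5". For the intra-cluster correlation it says "We used a conservative estimate of 0.4 for this study", and it then states "The variance was adjusted for a design effect of 2.6 to account for the between-cluster variability". Table 17 gives two sets of limits, exact Poisson and a "normal approximation of the Poisson distribution accounting for a design effect".

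Protocol 5.1.1 describes two sampling routes. The default lists every household in the sampling area and draws a simple random sample. If the area is too large to list, "at least eight clusters of similar population size (blocks or streets) will be selected by simple random sampling", and households are then listed and sampled inside the selected units. In that section the word *cluster* means a block or street.

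The end of Protocol 9.2 gives a between-cluster variance formula for estimating the design effect at analysis. The only definition of the unit is "c is the number of clusters", with person-years and cases indexed by cluster.

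Protocol 6.5.2.1 records a household number in the eCRF. No section mentions a block or street identifier. SAP 9.2.2 uses an exact Poisson interval and says in its heading that clustering is not taken into account.

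**The concern.** In a two-stage sample, the variance of an overall rate is governed by how much the first-stage units differ. If eight blocks supply all 2,000 subjects, each holds about 2000/8 = 250 people, or 50 households of five. Differences in dengue rate between blocks then inflate the variance in a way that a household term cannot capture.

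The word *cluster* points to households in the planning part of Protocol 9.2 and to blocks or streets in 5.1.1. An analyst with only a household number in the data could reasonably run the formula on households. On the fallback route, that treats households in one block as independent.

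The primary result is an incidence rate, and Protocol 3.1 says the study is to supply incidence data for sizing later trials. A falsely narrow interval would pass straight into that work.

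**Working it through.** **1. Reproduce the plan.** D = 1 + (b − 1)ρ = 1 + (5 − 1) × 0.4 = 2.6. For 40 cases in 3,300 person-years (PY) the rate is 1.21 per 100 PY. The half-width is 1.96 × √(2.6 × 40)/33 = 0.61, giving 0.61 to 1.82 as in Table 17. All ten rows reproduce in both interval columns. No term refers to blocks or streets.

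**2. Add the missing stage.** Inputs from the documents: 8 blocks (the stated minimum), 2,000 subjects, 5 per household (so 400 households) and 3,300 PY. Assumptions, since the documents give no figures: household CV 2, block CV k from 0 to 1.0, gamma-distributed multiplicative effects, equal cluster sizes and 40 expected cases. The variance relative to simple Poisson is

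1 + 2² × (1 + k²) × 40/400 + k² × 40/8 = 1.4 + 5.4k².

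This gives 1.40, 1.74, 2.75, 4.05 and 6.80 at k = 0, 0.25, 0.5, 0.7 and 1.0.

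**3. Simulate the formula in Protocol 9.2 both ways** (10,000 replicates; repeat runs differ by one or two percentage points in coverage).

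| Block CV | True ratio | Household run: mean estimate, coverage | Block run, t on 7 df: mean estimate, coverage | Coverage using 2.6 | Coverage, exact Poisson |
|---|---|---|---|---|---|
| 0 | 1.40 | 1.40, 94% | 1.41, 94% | 99% | 91% |
| 0.25 | 1.74 | 1.43, 91% | 1.74, 94% | 98% | 89% |
| 0.5 | 2.75 | 1.51, 83–85% | 2.63, 93% | 93–94% | 79–80% |
| 0.7 | 4.05 | 1.60, 77% | 3.75, 91% | 87% | 69% |
| 1.0 | 6.80 | 1.77, 67–68% | 5.94, 88% | 75–76% | 58% |

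The household run barely reacts to block variation. The block run follows it, although eight units are few and coverage falls to 88% at CV 1.0.

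**4. What this does to the interval.** At 40 cases and block CV 0.5, the household run gives a half-width of about 1.96 × √(1.51 × 40)/33 = 0.46 per 100 PY. The true variance with a t quantile of 2.365 gives 2.365 × √(2.75 × 40)/33 = 0.75.

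**5. Where 2.6 stops being enough.** Setting 1.4 + 5.4k² = 2.6 gives k = 0.47. The slack comes from the household part: without block variation the ratio is 1.4, which matches 1 + 4ρ at ρ = 0.1 rather than the planned 0.4. If ρ really were 0.4, there would be no slack and any block variation would push D above 2.6. The break-even also depends on the number of cases. The same calculation gives k of about 1.05 at 10 cases (1.1 + 1.35k² = 2.6) and 0.35 at 60 cases (1.6 + 8.1k² = 2.6).

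**6. More blocks.** With 32 blocks (assumed), the ratio at k = 0.5 is 1 + 0.5 + 0.25 × 40/32 = 1.81 instead of 2.75.

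**The case against.** The point depends on a route that may never have been taken. Full-list household sampling is the default, and a household design effect fits it. Eight is a minimum and, since each site compiles its own list, it appears to apply per site, so 250 subjects per block is an upper bound. The formula could already be meant for blocks, because 5.1.1 reserves the word *cluster* for them. All of this stands, and it makes the point conditional. It also shows why the unit has to be named.

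A reader might go further and infer that Table 17 overstates precision wherever blocks were used. Adding the block term to the full 2.6 gives D = 2.6 + k² × 40/8, which is 3.85 at CV 0.5 and 7.6 at CV 1.0, with coverage of about 89% and 75%. The documents do not support that as a general statement. It holds the household correlation at a value the protocol itself calls conservative, and even this stacked form gives only 2.91 at CV 0.25. With weaker household clustering, 2.6 still covers 93–94% at CV 0.5.

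A reader might also take the tertiary endpoint on cases near an index household as evidence of large block differences. It is a descriptive endpoint about short distances and two-week windows. It says nothing about the spread of two-year rates between blocks.

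Finally, the SAP applies no design effect at all, so its interval is too narrow before this question arises. That is true. But bringing the protocol's formula back at household level would not repair the interval on the two-stage route.

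**Conclusion.** The point holds in conditional form. The 2.6 reflects households only, and the analysis-time formula leaves its unit open. If blocks or streets were sampled first, a household-level estimate understates the variance whenever blocks differ. Under the assumptions shown, coverage is about 91%, 83–85% and 67–68% at block CVs of 0.25, 0.5 and 1.0. On the full-list route there is no fault of this kind.

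Table 17 is adequate at 40 cases up to a block CV of about 0.5 and too narrow above that. This rests on household clustering weaker than ρ = 0.4. The documents fix neither the block CV nor the number of blocks actually used, so these figures show a range and are not an estimate for this study.

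The analyses are descriptive with no success criterion, so no decision rule is affected. What is affected is the stated uncertainty of the primary rate.

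**What to change.** 1. State in the SAP which sampling route each site used and, if two-stage, how many blocks or streets were drawn. SAP section 2 describes enrolment in the past tense, so this should be known.
2. In the design-effect formula of Protocol 9.2, define the index i and the count c as the block or street where two-stage sampling was used, and as the household only where households came from a full list. Use a t quantile on c − 1 degrees of freedom.
3. SAP 9.2.2 contains no cluster formula, so the variance has to be written in. Replace the unadjusted exact Poisson interval with one based on this variance, or report the two side by side.
4. Note in Protocol 9.2 that 2.6 and Table 17 reflect household clustering only.

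The cost is wording, carrying a block identifier from the household listing into the analysis data, and a few lines of code. The price in the results is somewhat wider intervals and, with eight blocks, only seven degrees of freedom. Even then the block-level interval falls somewhat short of 95% if blocks differ strongly (about 88% at CV 1.0), which the report should acknowledge.

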9.10. Conduct of analyses

Any deviation(s) or change(s) from the original statistical plan outlined in this protocol will be described and justified in the final study report.

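### The protocol's formula for estimating rho divides by person-years per cluster, while the planning formula counts subjects per household, so the estimate cannot be compared with the assumed 0.4

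*Protocol*

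**What the plan says.** Protocol section 9.2 uses ρ twice.

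- **Planning.** The design effect is D = 1 + (b − 1)ρ, where b "is the average number of subjects sampled per household". The inputs are stated: "Here we assumed b to be 5" and, for ρ, "We used a conservative estimate of 0.4 for this study". The result is D = 2.6, which Table 17 uses.
- **Analysis.** DE is the ratio of a cluster-sample variance to a simple-random-sample variance. The terms x_i and y_i "are the number of person-years and the number of cases, respectively in the" i-th of c clusters. The intra-cluster correlation "may then be estimated as" ρ = (DE − 1)/[(Σx_i/c) − 1].

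The analysis formulas do not repeat what a cluster is. The definition of b points to the household. Protocol section 5.1.1 allows a first stage of blocks or streets: "If the sampling area is too large to compile a list of all households", at least eight such clusters are drawn before households are listed.

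The SAP has no step for ρ or DE. The title of its section 9.2.2 is "The method for estimating the CIs for incidence rate not accounting for clustered data", and the interval given there is exact Poisson.

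**The concern.** The second formula is the first one solved for ρ, so the cluster size should be the same quantity in both. In the first it is a count of subjects. In the second it is a sum of follow-up time, because Σx_i/c is the mean person-years per cluster. Applied to the plan's own inputs, the second formula should return 0.40, and it does not.

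Two misuses are possible if ρ is reported:

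- The value may be read against the assumed 0.4 and seem to show that the assumption was cautious, when clustering was in fact as strong as planned or stronger.
- The value may be carried into a later sample-size calculation with b in subjects. Protocol section 3.1 names sample-size calculation for future efficacy trials as a purpose of the study's incidence data.

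**Working it through.** **Inputs (protocol section 9.2).** b = 5, ρ = 0.4, D = 2.6, 2,000 subjects, 3300 person-years. The section also mentions 3,000 subjects in one sentence; 2,000 is used here because it agrees with section 5.1 and the synopsis.

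**Plan's own figures.**
- D = 1 + (5 − 1) × 0.4 = 2.6, as stated.
- All ten rows of Table 17 reproduce to two decimals: exact Poisson limits, and n/PY ± 1.96 × √(2.6n)/PY with the lower limit cut at 0.
- Drop-out of 10% and then 20% gives 2000 × 0.9 + 2000 × 0.9 × 0.8 = 3240 person-years, close to the stated 3300.

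**Analysis formula at the planned inputs, household as cluster.**
- Person-years per subject: 3300/2000 = 1.65
- Person-years per household: 5 × 1.65 = 8.25
- ρ with person-years: (2.6 − 1)/(8.25 − 1) = 1.6/7.25 = 0.22
- ρ with subjects: (2.6 − 1)/(5 − 1) = 1.6/4 = 0.40

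The ratio of the two is 4/7.25 = 0.55 at any DE.

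**Sensitivity to person-years (DE 2.6, equal households of 5).**

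| Person-years | Subjects | Per household | ρ as written |
|---|---|---|---|
| 3240 (drop-out arithmetic) | 2,000 | 8.10 | 0.225 |
| 3300 (stated) | 2,000 | 8.25 | 0.221 |
| 4000 (no drop-out) | 2,000 | 10.0 | 0.178 |
| 3300 | 3,000 (the stray count) | 5.5 | 0.356 |

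**Reuse.** 1 + 4 × 0.2207 = 1.88 instead of 2.6. The standard error is then √(1.88/2.6) = 0.85 of what it should be, about 15% too small. The formula as written returns 0.40 only at DE = 1 + 0.4 × 7.25 = 3.9, where the interval is √(3.9/2.6) = 1.22 times as wide as planned.

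**Is DE itself affected?** Hardly. With equal households and equal follow-up, let p be the rate per person-year and q = 1.65p the risk per subject. The variance ratio is then 2.6 × (1 − q)/(1 − p), which is 2.60 to 2.57 over Table 17's overall rates of 0.30 to 1.82 per 100 person-years. The fault lies in the divisor for ρ.

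**Simulation (beta-binomial, true ρ 0.40, 400 households of 5, mean follow-up 1.65 years).** Replicates with fewer than 2 cases were excluded.

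| Expected cases | ρ as written | ρ with subjects |
|---|---|---|
| 10 | 0.19 | 0.34 |
| 30 | 0.21 | 0.38 |
| 60 | 0.21 | 0.39 |

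A second run with constant follow-up gave subject-based means (SD) of 0.36 (0.20), 0.38 (0.11) and 0.39 (0.08).

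**Unequal households (assumed sizes 3 to 7, larger simulated samples).** As written 0.24 to 0.25; with subjects 0.43 to 0.45. The gap remains.

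**The case against.** The strongest reply is that nothing planned depends on this. ρ is optional, no objective or endpoint uses it, and the SAP does not compute it. Harm requires someone to report ρ without its size term and a reader to combine it with a different one. Anyone with DE and subjects per household can recover 0.40. This stands, and it is why severity is low.

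The analysis formula is also consistent with itself: 1 + 7.25 × 0.2207 = 2.6. No printed figure is wrong. That is true, but the section uses one symbol for both quantities and calls both the intra-cluster correlation, so a reader has no warning that they differ.

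The value 0.22 is conditional. It needs household clusters of 5, a realised DE of 2.6 and 1.65 person-years per subject. With eight blocks as clusters (an assumed case, DE 2.6), the values would be 1.6/(3300/8 − 1) = 0.0039 in person-years and 1.6/(2000/8 − 1) = 0.0064 in subjects. The planning value of 0.40 would then no longer be the comparator.

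Sampling error also matters. At about 10 cases the subject-based estimate has an SD of about 0.20, which exceeds the gap between the two versions (0.36 against 0.20). One realised value could not reveal the discrepancy there; at 60 cases it would be clear.

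The dependence on the time unit can be pressed further by converting to person-months. The documents fix the unit as years, so that describes no planned analysis.

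**Conclusion.** The formula is wrong as written, with low severity. At the plan's inputs, with the household as cluster, it returns about 0.22 instead of 0.40, and 0.18 to 0.23 over plausible person-year totals for 2,000 subjects in equal households. Reused with b = 5, 0.22 implies a design effect of 1.88 instead of 2.6.

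A reader might infer three stronger things that the documents do not support:

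- *The planned precision is miscalculated.* It is not: 2.6 and Table 17 reproduce.
- *The estimated design effect or the reported incidence interval will be biased by this slip.* DE barely changes with the unit, and the SAP's exact Poisson interval uses neither DE nor ρ. Whether the SAP should use DE is a separate question.
- *The study will report 0.22.* That figure holds only at the planned inputs, the ρ step is optional, and the documents do not say whether the household or the block/street was the sampled cluster.

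**What to change.** Keep person-years in the variance ratio for DE. If ρ is reported:

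- Compute ρ = (DE − 1)/(m − 1), with m the mean number of enrolled subjects per cluster.
- Name the cluster actually sampled: the household, or the block or street if the option in section 5.1.1 was used. Define m and b for that same cluster.
- Define m and b in the same way. With assumed household sizes spread evenly over 2 to 8 and 60 cases (simulated DE 2.83), the simple mean (5.0) gives ρ 0.46 and the size-weighted mean Σm_i²/Σm_i (5.8) gives 0.38. Each returns DE with its own b (1 + 4.0 × 0.46 = 2.84; 1 + 4.8 × 0.38 = 2.82), but mixing them does not (1 + 4.0 × 0.38 = 2.52).
- Report ρ with its uncertainty, above all if cases are few.

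Otherwise report DE only, with the cluster named.

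The cost is a sentence or two in the SAP or the final study report, with no new data and no protocol amendment. Protocol section 9.10 already provides that changes "from the original statistical plan outlined in this protocol will be described and justified in the final study report".
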